## **15.10. Statistical Model and Analyses of Secondary Endpoint(s)**

### **15.10.1.1. Secondary Endpoint for ZEUS Algorithm**

Within each block of 16, secondary endpoints (a total of 176) will be evaluated in a fixed sequence of testing for adjustment of multiplicity. The results will be compared to the iCGM Special Control criteria for sensor accuracy (SG limit of 50-400 mg/dL). For each of the endpoints, iCGM measurement refers to the sensor glucose value:

- % of iCGM measurements that indicate a positive glucose rate of change greater than 1 mg/dL/min when the corresponding true negative glucose rate of change is less than -2 mg/dL/min as determined by the corresponding blood glucose measurements
- % of iCGM measurements that indicate a negative glucose rate of change less than -1 mg/dL/min when the corresponding true positive glucose rate of change is greater than 2 mg/dL/min as determined by the corresponding blood glucose measurements
- Guardian™ Sensor (3) values will be compared to YSI™\* plasma glucose values during YSI™\* FSTs. A within 20% mean agreement rate between Guardian™ Sensor (3) values and YSI™\* plasma glucose values during YSI™\* FST days will be evaluated
- Guardian™ Sensor (3) values will be compared to YSI™\* plasma glucose values during YSI™\* FSTs. A within 15% mean agreement rate when SG >180 mg/dL between Guardian™ Sensor (3) values and YSI™\* plasma glucose values during YSI™\* FST days will be evaluated
- Guardian™ Sensor (3) values will be compared to YSI™\* plasma glucose values during YSI™\* FSTs. A within 40% mean agreement rate when SG >180 mg/dL between Guardian™ Sensor (3) values and YSI™\* plasma glucose values during YSI™\* FST days will be evaluated
- When iCGM values are greater than 180 mg/dL, corresponding blood glucose value read less than 70 mg/dL.
- Guardian™ Sensor (3) values will be compared to YSI™\* plasma glucose values during YSI™\* FSTs. A within 15% mean agreement rate when SG between 70 and 180 mg/dL between Guardian™ Sensor (3) values and YSI™\* plasma glucose values during YSI™\* FST days will be evaluated
- Guardian™ Sensor (3) values will be compared to YSI™\* plasma glucose values during YSI™\* FSTs. A within 40% mean agreement rate when SG between 70 and 180 mg/dL between Guardian™ Sensor (3) values and YSI™\* plasma glucose values during YSI™\* FST days will be evaluated
- When iCGM values are less than 70 mg/dL, no corresponding blood glucose value shall read above 180 mg/dL.

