- Guardian™ Sensor (3) values will be compared to YSI™\* plasma glucose values during YSI™\* FSTs. A within  $\pm 15$  mg/dL mean agreement rate when SG less than ( $<$ ) 70 mg/dL between Guardian™ Sensor (3) values and YSI™\* plasma glucose values during YSI™\* FST days will be evaluated
- Guardian™ Sensor (3) values will be compared to YSI™\* plasma glucose values during YSI™\* FSTs. A within  $\pm 40$  mg/dL mean agreement rate when SG less than ( $<$ ) 70 mg/dL between Guardian™ Sensor (3) values and YSI™\* plasma glucose values during YSI™\* FST days will be evaluated

Within each block of 16, secondary endpoints (a total of 176) will be evaluated in a fixed sequence of testing for adjustment of multiplicity. The results will be compared to the iCGM Special Control criteria for sensor accuracy (SG limit of 40-400 mg/dL). For each of the endpoints, iCGM measurement refers to the sensor glucose value:

- % of iCGM measurements that indicate a positive glucose rate of change greater than 1 mg/dL/min when the corresponding true negative glucose rate of change is less than -2 mg/dL/min as determined by the corresponding blood glucose measurements
- % of iCGM measurements that indicate a negative glucose rate of change less than -1 mg/dL/min when the corresponding true positive glucose rate of change is greater than 2 mg/dL/min as determined by the corresponding blood glucose measurements
- Guardian™ Sensor (3) values will be compared to YSI™\* plasma glucose values during YSI™\* FSTs. A within 20% mean agreement rate between Guardian™ Sensor (3) values and YSI™\* plasma glucose values during YSI™\* FST days will be evaluated
- Guardian™ Sensor (3) values will be compared to YSI™\* plasma glucose values during YSI™\* FSTs. A within 15% mean agreement rate when SG  $> 180$  mg/dL between Guardian™ Sensor (3) values and YSI™\* plasma glucose values during YSI™\* FST days will be evaluated
- Guardian™ Sensor (3) values will be compared to YSI™\* plasma glucose values during YSI™\* FSTs. A within 40% mean agreement rate when SG  $> 180$  mg/dL between Guardian™ Sensor (3) values and YSI™\* plasma glucose values during YSI™\* FST days will be evaluated
- When iCGM values are greater than 180 mg/dL, corresponding blood glucose value read less than 70 mg/dL.

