7.9 Evaluation of Objectives

7.9.1 Primary Endpoints

A total of 16 primary endpoints will be independently evaluated in blocks of 16 in the study. Analysis will be done in the blocks of 16 as:

- Adult (18 – 80 years), abdomen insertion location and 0 Calibration of Zeus algorithm
- Adult (18 – 80 years), abdomen insertion location and two Calibrations of Zeus algorithm (first calibration at 2 hours after insertion and second calibration at 8 hours after first calibration)
- Adult (18 – 80 years), abdomen insertion location and three Calibrations of Zeus algorithm (first calibration at 2 hours after insertion, second calibration at 8 hours after first calibration, and 14 hours after second calibration)
- Adult (18 – 80 years), abdomen insertion location and daily Calibrations of Zeus algorithm (first calibration at 2 hours after insertion, second calibration at 8 hours after first calibration, 14 hours after second calibration and 24 hours after the previous calibration until end of wear)
- Adult (18 – 80 years), arm insertion location and 0 Calibration of Zeus algorithm

- Adult (18 – 80 years), arm insertion location and two Calibrations of Zeus algorithm (first calibration at 2 hours after insertion and second calibration at 8 hours after first calibration)
- Adult (18 – 80 years), arm insertion location and three Calibrations of Zeus algorithm (first calibration at 2 hours after insertion, second calibration at 8 hours after first calibration, and 14 hours after second calibration)
- Adult (18 – 80 years), arm insertion location and daily Calibrations of Zeus algorithm (first calibration at 2 hours after insertion, second calibration at 8 hours after first calibration, 14 hours after second calibration and 24 hours after the previous calibration until end of wear)
- Peds (2 to 17 years), buttock insertion location and 0 Calibration of Zeus algorithm
- Peds (2 to 17 years), buttock insertion location and two Calibrations of Zeus algorithm (first calibration at 2 hours after insertion and second calibration at 8 hours after first calibration)
- Peds (2 to 17 years), buttock insertion location and three Calibrations of Zeus algorithm (first calibration at 2 hours after insertion, second calibration at 8 hours after first calibration, and 14 hours after second calibration)

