7.9.2 Secondary Endpoints

Within each block of 16, secondary endpoints (a total of 176) will be evaluated in a fixed sequence of testing for adjustment of multiplicity. The results will be compared to the iCGM Special Control criteria for sensor accuracy (SG limit of **50-400** mg/dL). For each of the endpoints, iCGM measurement refers to the sensor glucose value:

- % of iCGM measurements that indicate a positive glucose rate of change greater than 1 mg/dL/min when the corresponding true negative glucose rate of change is less than -2 mg/dL/min as determined by the corresponding blood glucose measurements
- % of iCGM measurements that indicate a negative glucose rate of change less than -1 mg/dL/min when the corresponding true positive glucose rate of change is greater than 2 mg/dL/min as determined by the corresponding blood glucose measurements
- Guardian™ Sensor (3) values will be compared to YSI™* plasma glucose values during YSI™* FSTs. A within 20% mean agreement rate between Guardian™ Sensor (3) values and YSI™* plasma glucose values during YSI™* FST days will be evaluated
- Guardian™ Sensor (3) values will be compared to YSI™* plasma glucose values during YSI™* FSTs. A within 15% mean agreement rate when SG > 180 mg/dL between Guardian™ Sensor (3) values and YSI™* plasma glucose values during YSI™* FST days will be evaluated
- Guardian™ Sensor (3) values will be compared to YSI™* plasma glucose values during YSI™* FSTs. A within 40% mean agreement rate when SG > 180 mg/dL between Guardian™ Sensor (3) values and YSI™* plasma glucose values during YSI™* FST days will be evaluated

- When iCGM values are greater than 180 mg/dL, corresponding blood glucose value read less than 70 mg/dL.
- Guardian™ Sensor (3) values will be compared to YSI™* plasma glucose values during YSI™* FSTs. A within 15% mean agreement rate when SG between 70 and 180 mg/dL between Guardian™ Sensor (3) values and YSI™* plasma glucose values during YSI™* FST days will be evaluated
- Guardian™ Sensor (3) values will be compared to YSI™* plasma glucose values during YSI™* FSTs. A within 40% mean agreement rate when SG between 70 and 180 mg/dL between Guardian™ Sensor (3) values and YSI™* plasma glucose values during YSI™* FST days will be evaluated
- When iCGM values are less than 70 mg/dL, no corresponding blood glucose value shall read above 180 mg/dL.

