- Guardian™ Sensor (3) values will be compared to YSI™* plasma glucose values during YSI™* FSTs. A within ± 15 mg/dL mean agreement rate when SG less than ($<$) 70 mg/dL between Guardian™ Sensor (3) values and YSI™* plasma glucose values during YSI™* FST days will be evaluated
- Guardian™ Sensor (3) values will be compared to YSI™* plasma glucose values during YSI™* FSTs. A within ± 40 mg/dL mean agreement rate when SG less than ($<$) 70 mg/dL between Guardian™ Sensor (3) values and YSI™* plasma glucose values during YSI™* FST days will be evaluated

Within each block of 16, secondary endpoints (a total of 176) will be evaluated in a fixed sequence of testing for adjustment of multiplicity. The results will be compared to the iCGM Special Control criteria for sensor accuracy (SG limit of **40-400** mg/dL). For each of the endpoints, iCGM measurement refers to the sensor glucose value:

- % of iCGM measurements that indicate a positive glucose rate of change greater than 1 mg/dL/min when the corresponding true negative glucose rate of change is less than -2 mg/dL/min as determined by the corresponding blood glucose measurements
- % of iCGM measurements that indicate a negative glucose rate of change less than -1 mg/dL/min when the corresponding true positive glucose rate of change is greater than 2 mg/dL/min as determined by the corresponding blood glucose measurements
- Guardian™ Sensor (3) values will be compared to YSI™* plasma glucose values during YSI™* FSTs. A within 20% mean agreement rate between Guardian™ Sensor (3) values and YSI™* plasma glucose values during YSI™* FST days will be evaluated
- Guardian™ Sensor (3) values will be compared to YSI™* plasma glucose values during YSI™* FSTs. A within 15% mean agreement rate when SG > 180 mg/dL between Guardian™ Sensor (3) values and YSI™* plasma glucose values during YSI™* FST days will be evaluated

- Guardian™ Sensor (3) values will be compared to YSI™* plasma glucose values during YSI™* FSTs. A within 40% mean agreement rate when SG >180 mg/dL between Guardian™ Sensor (3) values and YSI™* plasma glucose values during YSI™* FST days will be evaluated
- When iCGM values are greater than 180 mg/dL, corresponding blood glucose value read less than 70 mg/dL.

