7.9.8 Comparison of CGM Performance to Reference under conditions leading to Alert

The alert will be triggered when the sensor BG value reaches the threshold glucose value. Predictive alerts will be evaluated by using the predicted sensor BG value based on current sensor BG and sensor BG readings within the previous 30 minutes.

In the in-clinic portion, the threshold and predictive alert analysis will be performed retrospectively with theoretical hypoglycemia threshold setting at 50 mg/dL, 60 mg/dL, 70 mg/dL, 80 mg/dL, 90 mg/dL and 100 mg/dL and theoretical hyperglycemia threshold setting at 180 mg/dL, 220 mg/dL, 250 mg/dL and 300 mg/dL.

The threshold alert performance will be evaluated for in-clinic portion by true alert rate, missed alert rate and false alert rate within 15 and 30 minute windows of the reference event. Predictive alert performance will only be evaluated for the in-clinic portion by true predictive alert rate, missed predictive alert rate and false predictive alert rate within 15 and 30 minute windows. All reference BG values will be used, including those less than (<) 40 mg/dL and greater than (>) 400 mg/dL.

The comparison of CGM performance to reference under conditions leading to alert will be evaluated by true alert rate, missed alert rate and false alert rate within 15 and 30 minutes window of the reference event.

The alert rates will be defined as follows:

Alert Rate Type	Column Label	Label Definition
Detection Rate	Hypo/Hyper Events Correctly Detected (%)	The device alarmed at the specified CGM settings within 30 minutes (or 15 minutes) before or after the reference blood glucose value (YSI™* or SMBG) goes below (for hypo) or above (for hyper) the specified CGM setting levels.

Alert Rate Type	Column Label	Label Definition
Missed Detection Rate	Hypo/Hyper Events Not Detected (%)	The device did not alarm at the specified CGM settings within 30 minutes (or 15 minutes) before or after the reference blood glucose value (YSI™* or SMBG) goes below (for hypo) or above (for hyper) the specified CGM setting levels.
True Alert	Alerts Verified by Hypo/Hyper Events (%)	There is at least one reference blood glucose value (YSI™* or SMBG) goes below (for hypo) or above (for hyper) the specified CGM setting levels within 30 minutes (or 15 minutes) before or after the sensor alarmed at the specified alert settings.

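### The SG limits also cut the mismatch rules: sensor 40-49 with glucose above 180 counts only in the 40-400 list, and sensor below 40 or above 400 counts in neither

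*SAP*

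**What the plan says.** SAP 7.9.2 and Protocol 15.10.1.1 give the same 11 secondary items twice. The first list is introduced with: "The results will be compared to the iCGM Special Control criteria for sensor accuracy (SG limit of 50-400 mg/dL". The second has the same header with a different range: "sensor accuracy (SG limit of 40-400 mg/dL".

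Counting the bullets in order, seven items are agreement rates (3-5, 7-8, 10-11), two concern rate of change (1-2), and two are mismatch rules. Item 6 reads: "When iCGM values are greater than 180 mg/dL, corresponding blood glucose value read less than 70 mg/dL". Item 9 reads: "When iCGM values are less than 70 mg/dL, no corresponding blood glucose value shall read above 180 mg/dL". Both mismatch rules appear in both lists.

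On testing, the SAP says: "Within each block of 16, secondary endpoints (a total of 176) will be evaluated in a fixed sequence of testing for adjustment of multiplicity". Neither document says which of the two lists decides success, or how the two sequences are ordered relative to each other.

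For the primary endpoint only, Protocol 15.8.2 (Pairing Scheme) states outright that sensor values outside 50-400 mg/dL are left out. The secondary headers use the term SG limit and do not say whether an out-of-range output is dropped, set to the limit, or counted as low or high.

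**The concern.** Item 9 is worded for any sensor value below 70 mg/dL and allows no exception. The header above it removes part of that range according to the test device's own reading. A sensor at 55 with YSI 200 breaks the rule. A sensor at 45 with YSI 200 is a larger error in the same direction, yet it lies outside the 50-400 version.

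A range limit has a rationale for percent or mg/dL agreement, where a numeric output inside the reporting range is needed. That rationale does not carry over to a mismatch rule: an output known to be below 50 is known to be below 70. Because item 9 tolerates no violation, dropping such pairs can only remove violations, never add them.

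The stake is a criterion that a single pair can decide. The two lists can also give opposite answers for the same block, and the plan does not say how to resolve that.

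**Working it through.** **Inputs.** Headers and items: SAP 7.9.2 and Protocol 15.10.1.1. Number of blocks: SAP 7.9.1, "A total of 16 primary endpoints will be independently evaluated in blocks of 16 in the study". Meaning of the range: Protocol 15.8.2.

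**The plan's own figure.** 2 age groups × 2 locations × 4 calibration schemes = 16 blocks. 16 blocks × 11 items = 176, which matches the stated total for each list. Two lists give 2 × 176 = 352 evaluations. Item 9 accounts for 2 × 16 = 32 of these, 16 under each limit.

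**Scope check.** Read the SG limit as an exclusion. A pair then counts against item 9 if lower limit ≤ SG ≤ 400, SG < 70 and reference > 180. A pair counts under item 6 if SG is within the limits, SG > 180 and reference < 70. With whole-number readings:

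| Sensor value | Reference | 50-400 list | 40-400 list | Smallest gap, mg/dL |
|---|---|---|---|---|
| 50-69 | above 180 | counted | counted | 181 − 69 = 112 |
| 40-49 | above 180 | not counted | counted | 181 − 49 = 132 |
| below 40 | above 180 | not counted | not counted | 181 − 39 = 142 |
| 181-400 | below 70 | counted | counted | 181 − 69 = 112 |
| above 400 | below 70 | not counted | not counted | 401 − 69 = 332 |

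The item 9 range therefore holds 69 − 50 + 1 = 20 whole-number sensor values in the first list and 69 − 40 + 1 = 30 in the second. With a reference of 190, SG 45 is missed by the first list and caught by the second; SG 39 and SG 35 are missed by both.

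**Is exclusion the right reading?** Protocol 15.8.2 uses the same 50-400 range explicitly to exclude values. The two secondary lists differ only in this limit, so the second list would add little unless the limit changes which readings enter. Exclusion is the natural reading, but it remains an inference.

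**What cannot be computed.** Neither document gives the number of readings below 50, below 40 or above 400, or the number paired with a reference on the opposite side. The 122-subject power simulation has no bearing on which readings are in scope.

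**The case against.** The strongest reply has four parts.

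1. The 40-400 list repeats item 9 for every block, so SG 45 with YSI 200 is counted there, and the difference between the two prespecified lists shows the effect of the 40-49 readings. This stands. A reader might infer that the worst false lows are never counted; for SG 40-49 that is wrong. It does not help below 40 or above 400.

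2. Analyses with no stated sensor limit would show such pairs: the error grids (SAP 7.9.6), the difference tables (SAP 7.9.4, where a 45/200 pair has a gap of 155 mg/dL, beyond the widest absolute band of 100) and the false-alert rates (SAP 7.9.8). These pairs would indeed be visible there. All three are descriptive, however, and none decides item 6 or item 9. A false alert is defined by the alert setting, not by a reference above 180. The alert section's statement "All reference BG values will be used, including those less than (<) 40 mg/dL and greater than (>) 400 mg/dL" concerns reference values, not sensor range.

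3. The secondary headers do not say that values are dropped. If a below-range output were set to the limit or counted as low, it would already be below 70 and item 9 would see it. That is correct, and it is why the reading is stated as an assumption. No text says that outputs are handled this way, so the plan needs the sentence in either case.

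4. The items refer to outside criteria, and an iCGM measurement is defined as the sensor glucose value. If the system reports no number outside its limits, there may be no value to mismatch. The documents do not say what the system reports there, so this cannot be settled from them. At the high end, a violation needs a gap of at least 332 mg/dL and may be very rare.

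**Conclusion.** The point holds in this form. With the SG limit read as an exclusion, the 50-400 version of item 9 can be met while pairs with SG 40-49 and YSI above 180 exist. Pairs with SG below 40 and YSI above 180, and pairs with SG above 400 and YSI below 70, are counted in neither list. For item 9 the selection acts in one direction, towards passing. The same is true of the violation count in item 6, although that item's wording sets no explicit tolerance.

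The size is unknown. A reader might assume a spread of sensor values within true violations and quote a percentage lost, or a probability of a false pass. The documents support no such spread. Independence between violations would also be doubtful, because samples are taken minutes apart from the same sensor. Three further inferences should be avoided: naming a 40-400 range does not show that readings of 40-49 occur; the bullets are not stated to be the testing order, so it is not established that a pass at item 9 opens items 10 and 11; and disagreement between the lists is possible, not shown.

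This should be corrected before analysis. It affects the scope of a secondary criterion, not the primary endpoint.

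**What to change.** In SAP 7.9.2 and Protocol 15.10.1.1:

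- Keep the 50-400 and 40-400 limits for the agreement items (3-5, 7-8, 10-11).
- For items 6 and 9, use every sensor output that has a paired YSI value. Count a below-range output as below 70 mg/dL and an above-range output as above 180 mg/dL.
- Tabulate out-of-range outputs against YSI for each block.
- State which list governs if the two disagree.

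The cost is wording in two documents and one extra table. Sensor values are produced after the study from stored raw data (Protocol 3.1), so no new data collection is needed. The downside is a possibly less favourable mismatch count.

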7.9.3 Numbers of Readings in the Low and High Ranges

Every effort to safely collect data in the low and high range via the hyperglycemic and hypoglycemic challenge will be made

7.9.4 Difference Tables Comparing Sensor and Reference Readings

Number and percentage of paired data points within 10%, 15%, 20%, 30%, 40%, 50%, 60%, 70%, 80%, 90% and 100% of the reference method (YSI™* for in-clinic portion and meter BG for home-use portion) will be summarized.

Number and percentage of paired data within 10 mg/dL, 15 mg/dL, 20 mg/dL, 30 mg/dL, 40 mg/dL, 50 mg/dL, 60 mg/dL, 70 mg/dL, 80 mg/dL, 90 mg/dL and 100 mg/dL of the reference method (YSI™* for in-clinic portion and meter BG for home-use portion) will be summarized.

7.9.5 Sensor Calibration

Characteristics of Guardian™ Sensor (3) calibration will be evaluated by:

- Rate of change (less than (<)-4.0 mg/dL/min, -4.0 to -2.5 mg/dL/min, -2.5 to -2.0 mg/dL/min, -2.0 to -1.5 mg/dL/min, -1.5 to -1.0 mg/dL/min, -1.0 to +1.0 mg/dL/min, +1 to +1.5 mg/dL/min, +1.5 to +2.0 mg/dL/min, +2.0 to +2.5 mg/dL/min, +2.5 to +4.0 mg/dL/min, and greater than (>) +4.0 mg/dL/min).
- Rate of change arrows that are displayed to users
- First calibration SMBG value ranges (40 - 70 mg/dL, 70 - 180mg/dL and 180 - 400 mg/dL): the numerical SGV accuracy will be evaluated against YSI™* stratified by the first calibration SMBG value up to the second calibration SMBG.

7.9.6 Clarke Error Grid Analysis (EGA) of Paired Sensor and YSI™* and Reference Values

1) Description

Clarke Error Grid Analysis (EGA) separates paired observations into five zones of clinical significance. The presence and severity of possible treatment error based on interstitial glucose assay evaluated by the sensor defines the five zones. Zone A represents the absence of treatment error, where the evaluation method and the reference method are within 20% of one another or in which both methods indicate hypoglycemia. Zone B represents cases where the two methods disagree by more than 20%, but do not lead to treatment error. Zones C, D, and E represent increasingly large and potentially harmful discrepancies between the evaluation and the reference method. If the method under evaluation has a high percentage (greater than (>)90%) of its pairs in Zones A and B, then it is considered clinically acceptable [Clarke et al, 1987].

2) Statistical analysis

Summary statistics (N, %) for each of the zones, as well as combined Zones A and B, will be calculated.

In order to evaluate differing levels of accuracy at various YSI™* defined glucose levels, the number and percentage of paired observations falling into Zones A, B, A+B, C, D, and E will be provided by YSI™* glucose ranges of 40-80 mg/dL, greater than (>) 80-120 mg/dL, greater than (>) 120-240 mg/dL, and greater than (>) 240 mg/dL.

All analysis performed using the Clarke Error Grid comparing the paired sensor and YSI™* reference glucose values will be duplicated using the Continuous Error Grid [Clarke et al, 1987] and the Consensus Error Grid [Parkes et al, 2000].

